7.7 Patient reported outcomes

Patient reported outcomes as described in [Section 6.2](#) will be analysed at Visit 1 for the Enrolled Set and at Visit 1, Visit 2 and Visit 3 for the Follow-up Set following the procedures described in [Section 7.1](#).

7.8 Non-HF medication

Prior non-HF medication is defined as any non-HF medication with start date prior to Visit 1, concomitant non-HF medication is either any prior non-HF medication which is ongoing at Visit 1 or any non-HF medication with start date between Visit 1 (including date of Visit 1) and Visit 3 (including date of Visit 3).

Prior non-HF medication will be displayed for the Enrolled Set and the Follow-up Set, concomitant medication only for the Follow-up Set following the procedures described in [Section 7.1](#).

Reasons for non-HF medications will be listed by patient and non-HF medication.

7.9 Safety analysis

7.9.1 Adverse events

All AEs documented in the eCRF will be analysed. Incidence rates of AEs, serious AEs, fatal AEs and AEs related to study procedures will be displayed by SOC and PT for the Follow-up set without any stratification.

In addition, a comprehensive listing of all AEs will be provided.

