3.1 Study design

This is an international, prospective, low-interventional study enrolling patients with chronic heart failure with reduced ejection fraction (LVEF \leq 40%) who are managed in the primary care setting across Europe. The study comprises three visits over a period of maximum 10 months. Enrollment is planned to last 24 months.

At baseline (**visit 1**) for all consecutive patients, who satisfy the inclusion and exclusion criteria, the demographic and clinical characteristics, their current therapy regimen for the treatment of HF, any concomitant medication and their baseline QoL (EQ-5D and KCCQ questionnaires) will be documented. At this visit, after the investigator documents his/her decision whether the patient is considered being clinically stable*, all patients (clinically stable and not stable) will have a blood test for assessing NT-proBNP levels.

[figure not shown]
Only patients who are considered being clinically stable* by the investigator and who show NT-proBNP blood levels \geq 600 pg/ml will enter the prospective period of the study.

Patients, who do not fulfill these criteria, i.e. are either not meeting the above definition of clinical stability or who show NT-proBNP levels $<$ 600 pg/ml will not continue further into the study and will have their end-of study documentation at the baseline visit.

Clinically stable patients with NT-proBNP levels \geq 600 pg/ml will be referred to a cardiologist for evaluation of their HF treatment. After the referral visit to the specialist's office, the patient will return within a suggested time window of up to 4 weeks after the cardiologist visit to the primary care physician for **visit 2**. During visit 2 the primary care physician will evaluate and record the recommendations provided or treatment changes introduced by the specialist and will make and record his/her decision on the patient's future HF treatment. There is no minimal visit time window for the timing of visit 2, as referral policies differ between different European countries and healthcare systems. However, visit 2 should be performed no later than 6 months after the baseline visit. Within this time frame, the exact timing will be managed by the primary care physician according to his/her practice and local organizational models.

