3.6 Risks and benefits

The risk to subjects in this trial will be minimized by compliance to the eligibility criteria. Blood sampling for NT-proBNP measurements will be performed at the baseline visit and at Visit 3 (for patients who enter the prospective period of the study), which bears minimal risks for the patient, associated with the sampling procedure (venous puncture). Other study procedures are observational, i.e. the investigators should follow and document their local clinical routine for the treatment and follow-up of patients with CHF. There is no investigational medicinal product and no drug/device treatment that is required by the protocol. Therefore the risks associated to this study, besides those associated to the venous blood sampling procedure, are comparable to those in a usual primary care setting.

4 Population

The study population will consist of adult (≥ 18 years) male and female patients with chronic heart failure with reduced ejection fraction (LVEF $\leq 40\%$) who are currently managed in a primary care setting in sites across Europe. Provided the below inclusion and exclusion

criteria are met, all consecutive CHF patients at a given site will be documented and will be subject to NT-proBNP measurement at baseline. Prior to measuring NT-proBNP at baseline, the physician must provide his/her judgement, whether the patient is considered as clinically stable based on the definition provided in [Section 2.1](#). Patients who do not meet the definition of being clinically stable at baseline and/or patients who show NT-proBNP levels < 600 pg/ml at baseline will not enter the prospective period of the study, but their baseline information will be documented. Patients who enter the prospective period of the study, as defined as clinically stable patients with NT-proBNP levels \geq 600 pg/ml will be referred to a cardiologist and will return to the site 2 more times (Visit 2 and Visit 3) for follow-up documentation.

It is planned to enroll a total of 4,000 CHF patients of which approximately 2,400 are estimated to enter the prospective period (are considered clinically stable and show NT-proBNP levels \geq 600 pg/ml). The recruitment will be regarded as completed once approximately 2,400 patients have entered the prospective period irrespectively how many patients have been enrolled totally.

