6.5 Safety

There are no safety endpoints within the objectives of this study and no study medication. Any adverse event will be recorded in the CRF after the patient has provided his/her informed consent, including adverse events that are related to study procedures (e.g. NT-proBNP assessments). In addition, the below variables, if available, will be documented at baseline and Visit 2 and Visit 3 (as applicable) to describe the clinical features of the patients. Adverse drug reactions (ADR) shall be reported to the authorities following local laws and regulations ([Section 7](#)).

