9.5.2 Safety variables

Adverse events (AEs) will be coded by means of the Medical Dictionary for Regulatory Activities (MedDRA). Incidence rates of AEs and Serious Adverse Events (SAEs) due to study related procedures based on “preferred terms” and “system organ class” will be displayed. Additionally, all AEs will be individually listed.

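### SAP 7.9.1 tabulates procedure-related adverse events only in the Follow-up Set, although every enrolled patient has the study blood draw at Visit 1

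*SAP*

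**What the plan says.** SAP 7.9.1 opens broadly: "All AEs documented in the eCRF will be analysed". The next sentence covers the incidence of AEs, serious AEs, fatal AEs and AEs related to study procedures, which "will be displayed by SOC and PT for the Follow-up set without any stratification". The section then adds: "In addition, a comprehensive listing of all AEs will be provided".

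SAP section 5 defines the Follow-up Set as the patients referred to the cardiologist. SAP 7.9.2, the next subsection, covers vital signs, heart failure signs and symptoms, and laboratory values. It uses the Enrolled Set at Visit 1 and the Follow-up Set at Visits 1 to 3.

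On exposure, protocol 3.1 says that at baseline "all patients (clinically stable and not stable) will have a blood test for assessing NT-proBNP levels". Protocol 3.6, which names venous sampling as the risk specific to the study, says: "Blood sampling for NT-proBNP measurements will be performed at the baseline visit and at Visit 3". The Visit 3 draw applies only to patients in the prospective period.

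On collection, protocol 6.5 says: "Any adverse event will be recorded in the CRF after the patient has provided his/her informed consent". It makes clear that events caused by the study's own procedures count. On reporting, protocol 9.5.2 promises "Incidence rates of AEs and Serious Adverse Events (SAEs) due to study related procedures" and names no analysis set. Its parent section, 9.5, assigns secondary variables to the Follow-up Set.

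**The concern.** The draw is the only invasive procedure the protocol imposes, and the protocol treats other risks as those of usual primary care. A rate of procedure-related events should therefore have as its denominator everyone who underwent the procedure. SAP 7.9.1 instead uses patients who were considered stable, had NT-proBNP of at least 600 pg/ml and were then referred. Someone who was sampled at Visit 1 and went no further contributes to neither the numerator nor the denominator. This holds for patients who were unstable, had a low NT-proBNP, or were suitable but not referred.

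At stake is whether the report gives the rate promised in protocol 9.5.2 for the whole exposed population, or leaves the reader to rebuild it from a listing. The primary analysis is not affected.

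**Working it through.** **Inputs**

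- 1,728 patients for the primary estimate, 20% adherent at baseline, 2,160 prospective patients required, 60% with NT-proBNP ≥ 600 pg/ml, 10% drop-out, 4,000 enrolled, 2,400 prospective (protocol 9.8; totals also in protocol section 4 and SAP 4.2).
- One draw at Visit 1 in all patients, and a second at Visit 3 in prospective patients (protocol 3.1 and 3.6).

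**1. Reproduce the planned totals.**

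- 1,728 / 0.80 = 2,160
- 2,160 / 0.60 = 3,600
- 3,600 / 0.90 = 4,000 enrolled
- 2,160 / 0.90 = 2,400 prospective

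The protocol's figures are reproduced.

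**2. Share of sampled patients outside the table.**

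(4,000 − 2,400) / 4,000 = 1,600 / 4,000 = 40%.

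**3. Share counted by draws.**

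Planned draws = 4,000 + 2,400 = 6,400. Draws in patients outside the Follow-up Set = 1,600. Share = 1,600 / 6,400 = 25%. This assumes that every prospective patient has the Visit 3 draw. SAP 4.2 says that not everyone could reach Visit 3, and each missed draw raises this share.

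**4. Sensitivity to clinical stability.**

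The 60% covers NT-proBNP only, but entry also requires clinical stability, for which the documents give no rate. As an assumption, let a proportion s be stable, independently of NT-proBNP. The share outside is then 1 − 0.60 × s:

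| s (assumed) | Share of patients outside |
|---|---|
| 100% | 40% |
| 90% | 46% |
| 80% | 52% |
| 70% | 58% |

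**5. Precision if no procedure-related event is seen.**

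The exact one-sided 95% upper bound is 1 − 0.05^(1/N):

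- N = 2,400: 1 − 0.05^(1/2,400) = 0.00125, or 0.125%
- N = 4,000: 1 − 0.05^(1/4,000) = 0.00075, or 0.075%

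The difference is 0.05 percentage points. These are bounds per patient. They treat all patients as equally well observed, which is generous to the larger denominator: protocol 3.1 ends documentation at the baseline visit for patients who do not enter the prospective period.

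**6. Sets used in the two safety subsections.**

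| SAP section | Variables | Set at Visit 1 |
|---|---|---|
| 7.9.1 | AEs, serious, fatal, procedure-related | Follow-up Set only |
| 7.9.2 | Vital signs, HF signs and symptoms, laboratory values | Enrolled Set and Follow-up Set |

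The SAP also analyses NT-proBNP (7.6) and patient-reported outcomes (7.7) at Visit 1 in the Enrolled Set. Procedure-related AEs arising at Visit 1 are not treated in the same way.

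**The case against.** **The protocol prespecifies this set.** Safety variables are subsection 9.5.2, and 9.5 puts secondary variables in the Follow-up Set. This stands. A reader might infer that the SAP departs from the protocol, but it does not. Section 9.5.2 names no set itself, and the SAP already goes beyond 9.5 by using the Enrolled Set at Visit 1 for NT-proBNP and patient-reported outcomes. An added table would therefore fit the SAP's own practice.

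**Nothing is lost.** The listing covers all AEs, and SAP 7.2 reports the size of each analysis set, so the rate can be rebuilt by hand. This also stands, and on that reading the opening sentence of 7.9.1 can be squared with the next one. What is missing is the tabulated rate.

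**Selection bias.** The Follow-up Set depends partly on the result of the procedure being assessed, so a reader might infer a biased rate. The documents do not support that. Entry also depends on clinical stability, and nothing suggests that sampling complications vary with NT-proBNP level. A smaller denominator alone costs precision.

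**The 40% as a fact.** A reader might take it as the realised share. It is a planning figure. Recruitment and data collection stopped in March 2018 (SAP 4.2), and no actual counts are given.

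**Moving every AE table to the Enrolled Set.** This is tempting but wrong. It would pool patients whose participation ends at baseline with patients followed for up to 10 months, and so dilute the overall AE, SAE and fatal AE rates. For those rates the Follow-up Set is defensible.

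**Little depends on it.** The study has no safety endpoints and no study medication, and the protocol regards the draw as minimal risk. This is a fair reason to keep the point minor.

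**Conclusion.** The point holds as a small improvement, limited to procedure-related events. Followed as written, SAP 7.9.1 gives a procedure-related rate whose denominator leaves out a planned 1,600 of 4,000 sampled patients (40%; 25% of planned draws). The consequence is reduced completeness and a somewhat looser upper bound: about 0.125% against 0.075% with zero events.

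These figures rest on the planned totals, on full attendance at Visit 3 for the draw count, and on equal observation for the bounds. The 40% would be higher if a material share of patients were not clinically stable. Neither bias nor a breach of the protocol is shown, and the study's conclusions on guideline adherence are unaffected.

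**What to change.** In SAP 7.9.1, add one table of AEs and SAEs related to study procedures, by SOC and PT, in the Enrolled Set. Split it by inclusion in the prospective period, the stratifier already defined in SAP 7.1, so that patients with different observation times and numbers of draws are not pooled. Keep overall AE, SAE and fatal AE incidence in the Follow-up Set, with events in other patients in the listing. Reword the opening of 7.9.1 to say which AEs are tabulated in which set and which are only listed.

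The cost is one extra table from data already collected. Two limits should be footnoted. Patients outside the prospective period are observed only around Visit 1, so delayed events may be missed in them. SAP section 5 also restricts the analysis to patients with an NT-proBNP value, so anyone whose draw gave no result would be absent even from the Enrolled Set; the number of such patients should be stated.

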7.9.2 Other safety variables

Vital signs, signs and symptoms of HF including NYHA and Laboratory assessments others than NT-proBNP, as described in [Section 6.4](#), will be analysed at Visit 1 for the Enrolled Set and at Visit 1, Visit 2 and Visit 3 for the Follow-up Set following the procedures described in [Section 7.1](#).

7.10 Missing data and outliers

In General, no imputation of missing data will be performed for analysis of the primary variable. This means that for patients with missing LVEF at Baseline the primary variable is not evaluable. Instead, proportions based on observed data and proportions including patients with missing data will be provided (see [Section 7.4.2](#)). However, for reason of sensitivity the analyses of guideline adherence (only analyses taking into account the HF indication of treatments) will be repeated by applying the following substitution: missing LVEF values will be replaced by LVEF category “> 35%”.

Missing values in single items of patient questionnaires will be treated according to the descriptions in [Section 4.5.2](#). Changes from Baseline cannot be calculated if either the data at Visit 1 or after Visit 1 are missing: no replacement of missing data will be performed in such cases.

Incompletely reported date variables will be imputed as follows: if day is not given, the 15th of the month will be imputed, if month is not given the 1 July of the respective year will be used for analysis. If these imputations lead to negative values when calculating durations, the respective duration will be set to one day.

Any impossible / implausible values not identified during data management processes will be treated as missing and not to be imputed

7.11 Subgroup analyses

Adherence to ESC treatment in Follow-up Set (conditional analyses of A2 on guideline adherence level 1, calculation of percentages based on observed data), the frequency of cardiologist's advice on patient level and the acceptance of cardiologist's advice on patient level will be analysed for the following subgroups:

- Gender (Male, Female)
- Age groups (< 65, \geq 65 to < 75, \geq 75 to < 85, \geq 85 years)
- Duration of HF (< vs. \geq median)
- NT-proBNP level categories at Visit 1 (\geq 600 to < 1200 pg/ml, \geq 1200 to < 1800 pg/ml, \geq 1800 pg/ml)
- Country clusters (Western Europe: Norway, Denmark, Belgium, France, Spain, Portugal, Italy, Malta; Eastern Europe: Russia, Hungary, Poland, Lithuania, Latvia, Estonia, Cyprus, Croatia, Slovenia, Israel)

In addition, all analyses (including subgroup analyses without country specific subgroup analyses) will be performed separately for patients from Belgium study centres.

7.12 Further issues

Due to the exploratory character of the study, modifications and extensions of the pre-specified analyses are possible if indicated by the data. This will be documented in an analyses plan addendum.

In addition to the analysis based on the Enrolled Set and Follow-Up set, a separate analysis for patients in Belgium centres will be conducted. This analysis will be performed following the descriptions for the overall analysis in this SAP (exception: subgroup analysis by country clusters).

7.13 Deviations from the analysis planned in the study protocol

The described analyses deviate from the analyses planned in the study protocol in the following aspects:

- Analysis of HF medication will be performed by visit instead of using general classifications for "prior" and "concomitant". This enables interpretations of actual treatment status of patients without any overlay of specific treatment schemes. In addition, this analysis is consistent with the primary analysis which focusses on specific time-points.
- The results of the primary analysis were originally planned to be presented in terms of a cross table between A1 and A2. In order to increase readability and

clarity of the results, this cross table is now split up for the analysis providing the results in separate tables. The content of the primary analysis is not affected by this change.

- According to the study protocol, it was planned to perform all treatment analyses stratified by country: this was adapted to specified treatment analyses (see [Section 7.11](#)) in order to improve readability and clarity of the results.

8 References

2. Corrigendum to: '2016 ESC Guidelines for the diagnosis and treatment of acute and chronic heart failure'. *Eur Heart J* 2017.

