2.4 Objectives and related endpoints

Table 2-1 Objectives and related endpoints

OBJECTIVE	Endpoint Title, Description and Reporting Time Frame for analysis and Unit of Measure	Stat Analysis Section
Primary		
To assess if NT-proBNP measurement-guided cardiologist-referral of CHF patients, who are currently judged by their primary care physician as being clinically stable, leads to optimization of HF treatment, defined as adherence to level I-A treatment recommendations of the current ESC guidelines for the treatment of HF.	Title: Change of the proportion of clinically stable patients whose therapy regimen adheres to ESC guideline recommendations before and after specialist referral. Description: Assessment of patients' treatment regimen with respect to ESC guideline adherence at baseline (Visit 1) and after referral to a specialist (visit 2); the change between both visits will be calculated to reflect the proportion of patients for whom optimization was deemed necessary and implemented. For definitions of clinically stable patients and adherence to current ESC guidelines see Section 2.1 . Units of Measure: Bivariate absolute and relative frequency distributions including 95%-confidence intervals. Time Frame: Baseline, Visit 2	Section 9.4

OBJECTIVE	Endpoint Title, Description and Reporting Time Frame for analysis and Unit of Measure	Stat Analysis Section
Secondary		

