9.4.2 Statistical model, hypothesis, and method of analysis

The analysis yielding to the primary objective will be performed by estimating the proportion of patients who are switched to an ESC guideline recommendation-adherent regimen after referral to a cardiologist based on all referred patients whose treatment does not adhere to these recommendations. A respective 95%- confidence interval (CI) will be provided for this proportion.

Cross-tabulation between the variables A1 and A2 will be displayed showing further absolute and relative frequencies, including the proportion of patients being treated in accordance to the ESC guideline recommendations already at baseline (i.e. before referral), the proportion of patients receiving ESC guideline-adherent treatment after the referral to the cardiologist and the rate of patients who remain on a therapy regimen that does not adhere to ESC guideline-recommendations after referral over all patients without ESC guideline-adherent treatment. Respective 95%-CIs will be provided for the estimates.

The analysis of the primary endpoint will be performed in the Follow-up Set.

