7.4.2 Adherence to ESC guidelines (primary analysis)

For each patient, HF treatment at every visit will be classified with respect to adherence to ESC guidelines on level 1 and level 2 as outlined in [Section 4.5.1](#). Respective frequency distributions of adherence (yes, no) will be provided for the Follow-up Set for every visit.

The primary analysis will be performed on guideline adherence level 1 (as described in [Section 4.5.1](#)) as follows: based on the patients in the Follow-up Set treated not according to ESC guidelines at Visit 1, absolute and relative frequencies of A2 will be provided. The proportions within this analysis will be calculated twice, with and without considering missing values for A2. 95%-CIs will be provided for the proportions.

This analysis of A2 will be repeated for all patients in the Follow-up Set treated according to guidelines (level 1) at Visit 1.

For sensitivity, the analyses of A2 conditional to guideline adherence at Visit 1 will be repeated for guideline adherence level 2 (drug type and dose).

For the Enrolled Set, adherence to ESC guidelines (level 1 and level 2) will be analysed at Visit 1, additionally stratified by inclusion into the prospective period of the study.

In addition, the analyses of guideline adherence with respect to drug type will be repeated without taking into account the indication of the applied medications. This means, patients taking an ACEi, ARB, Beta-Blocker or MRA without HF indication will not automatically be classified as non-adherent in this analysis. Instead, these drugs will be included in the analysis and can contribute to a guideline adherent treatment of the patient.

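### The SAP omits the protocol's 95% confidence intervals for adherence before and after referral, and its list of deviations does not say so

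*SAP*

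**What the plan says.** **Protocol.** Section 9.4.2 first plans the switch proportion (non-adherent at baseline, adherent at Visit 2) with a 95% CI. It continues: "Cross-tabulation between the variables A1 and A2 will be displayed showing further absolute and relative frequencies". Among these frequencies it names the baseline proportion, "including the proportion of patients being treated in accordance to the ESC guideline recommendations already at baseline (i.e. before referral", then "the proportion of patients receiving ESC guideline-adherent treatment after the referral to the cardiologist", and thirdly the share of baseline non-adherent patients who stay non-adherent. It ends: "Respective 95%-CIs will be provided for the estimates". Table 2-1 titles the primary endpoint as a change in the adherent proportion from before to after referral, and gives its unit as "Bivariate absolute and relative frequency distributions including 95%-confidence intervals".

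**SAP.** Section 7.4.2 states: "Respective frequency distributions of adherence (yes, no) will be provided for the Follow-up Set for every visit". It then gives A2 (adherence at Visit 2) among patients non-adherent at Visit 1, calculated with and without missing A2, and adds: "95%-CIs will be provided for the proportions". The same analysis is repeated for patients adherent at Visit 1. Section 7.1 bases percentages on observed data for each parameter and calculates Clopper-Pearson intervals only where a later section describes them. Section 7.13 lists the split of the cross table as a deviation made for readability and says of it: "The content of the primary analysis is not affected by this change".

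**The concern.** The before and after proportions are the figures most readers will set side by side for an endpoint titled as a change in a proportion. The protocol promised intervals for both. In the SAP no sentence calls for them, and SAP 2.5 makes the SAP's methods binding for programming, so they would not be produced by default. A reader who checks the list of deviations would conclude that nothing had been removed.

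The second issue is the denominator. Protocol 9.4.3 bases the primary analysis on patients with both assessments. The by-visit table follows the general rule in SAP 7.1, so Visit 1 rests on everyone with A1 and Visit 2 on everyone with A2. If patients without A2 differ in baseline adherence from the rest, the two percentages can differ although no treatment changed.

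**Working it through.** **1. Which estimates survive the split**

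| Estimate in protocol 9.4.2 | Value reported in SAP | 95% CI specified in SAP |
|---|---|---|
| Switch proportion, A2 adherent given A1 non-adherent | Yes, 7.4.2 | Yes |
| Remaining non-adherent, given A1 non-adherent | Yes, 7.4.2 | Yes |
| Adherent at baseline | Yes, by-visit table | No |
| Adherent after referral | Yes, by-visit table | No |
| Joint A1 × A2 display, percentages on total N | Counts only, across two tables | No |

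**2. Inputs (protocol 9.8).** Baseline adherence 20%; adherence after referral 30%; switch proportion 25%; 1,728 patients for ±2%; 2,160 in the prospective period; 10% drop-out, giving 2,400 entrants.

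**3. The plan's own precision figure.** 2,160 × 0.80 = 1,728 patients non-adherent at baseline. Half-width = 1.96 × √(0.25 × 0.75 / 1,728) = 2.04 points, which rounds to the stated ±2%. The exact interval for 432/1,728 is 23.0–27.1%. It is the same whether the tables are joined or split.

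**4. Recovering the joint table.** Setting the two conditional tables on top of each other returns the cross table. At planning values:

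| | A2 adherent | A2 non-adherent | Total |
|---|---|---|---|
| A1 non-adherent | 432 | 1,296 | 1,728 |
| A1 adherent | 216 | 216 | 432 |
| Total | 648 | 1,512 | 2,160 |

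The second row follows from the 30% assumption: 0.30 × 2,160 = 648, and 648 − 432 = 216. The margins are 432/2,160 = 20% and 648/2,160 = 30%.

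**5. The omitted intervals (Clopper-Pearson, n = 2,160).**
- Before referral, 432/2,160: 18.3–21.8%.
- After referral, 648/2,160: 28.1–32.0%.

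For the change itself the measurements are paired. The discordant counts are 432 and 216, so the difference is (432 − 216)/2,160 = 10.0 points. Its standard error is √(648 − 216²/2,160)/2,160 = 1.16 points, and the Wald 95% CI is 7.7 to 12.3 points.

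**6. Effect of different denominators.** Assume 2,400 entrants, 480 adherent at Visit 1 (20%), 240 with A2 missing, and no treatment change in anyone.
- All 240 missing were non-adherent: Visit 2 reads 480/2,160 = 22.2%.
- Missingness unrelated to A1: 48 of the missing were adherent, so Visit 2 reads 432/2,160 = 20.0%, with no shift.
- All 240 missing were adherent: Visit 2 reads 240/2,160 = 11.1%.

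The two ends are bounds, not predictions.

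**The case against.** A reader might infer that the joint table has been lost, or that the sentence in SAP 7.13 is simply false. The documents support neither.

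- **Joint table.** The two conditional analyses in SAP 7.4.2 are the two rows of the cross table and carry absolute counts. All four cells can be recovered, and 7.13 discloses the split. What goes is the joint display, the percentages on total N and the marginal intervals.
- **The 7.13 sentence.** Protocol 9.4 defines the aim of the primary analysis as estimating the switch proportion, and 9.4.2 presents the cross-tabulation frequencies as additional. Read that way, the sentence is correct. It fails only if the primary analysis means every estimate in 9.4.2. Table 2-1 gives some support to the wider reading, because it defines the primary endpoint as a change in proportion, in bivariate form with intervals.
- **Denominators.** The mismatch comes from the by-visit table and the general missing-data rule, not from splitting the cross table, so it does not count against the 7.13 sentence. Missing A2 is already handled within each A1 group. Missing baseline LVEF, the one cause of non-evaluability that SAP 7.10 names, removes A1 and A2 together and creates no mismatch between visits.
- **An apparent rise.** It is tempting to quote only the 2.2-point rise. It needs every patient without A2 to have been non-adherent at baseline, which nothing in the documents supports. The opposite extreme is an 8.9-point fall, and unrelated missingness gives zero.

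The study is also descriptive, and the missing intervals can be computed from tabulated counts. All of this limits the importance of the point. It does not remove the gap: two intervals that the protocol promises are specified nowhere in the SAP, and the list of deviations does not mention them.

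**Conclusion.** The point holds as a minor reporting gap. The main estimate, the switch proportion with its CI, is unaffected. The 95% CIs for adherence before and after referral are missing from the SAP, their omission is not declared, and the two by-visit percentages need not describe the same patients.

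The interval widths in the working rest on planning values. Two features of the SAP mean that the real ones will differ. Section 4.2 reports that recruitment and data collection were stopped early, and the documents give no attained sample size. The planning proportions in protocol 9.8 also refer to drug and dose, whereas SAP 7.4.2 runs the primary analysis on drug type alone.

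The figure of 240 missing A2 takes the protocol's 10% drop-out as a stand-in. Some missing A2 is plausible. Visit 2 could fall up to 6 months after baseline, while the last first visit was on 7 March 2018 and data collection closed with the last visit on 23 March 2018. The SAP mentions only Visit 3 as affected. The documents do not show how missing A2 relates to baseline adherence, so neither the direction nor the size of any shift can be stated.

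**What to change.** 1. In SAP 7.4.2, add one A1 × A2 table for the Follow-up Set with cell counts, percentages on total N and a column for missing A2.
2. From the patients with both A1 and A2, report Visit 1 and Visit 2 adherence with Clopper-Pearson 95% CIs. Preferably add a paired 95% CI for the change, since two separate marginal intervals do not measure it.
3. In SAP 7.13, limit the sentence to the switch proportion and its interval. If the marginal intervals are not restored, list their omission as a deviation.

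Cost: one table and one sentence, using data already collected.
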